9.3 Follow-up of Adverse Events

Follow-up procedures may be different based on the nature (diagnosis, severity, seriousness) of the AE and will follow Profil’s SOP on (S)AE Handling and Reporting.

Clinical Trial Protocol				
Trial ID	EudraCT-No.	Date	Status / Version-No.	Page
I8B-MC-ITST	2019-003493-13	17 Jan 2020	Final 2.0	55 of 74

Non-serious AEs classified as severe or possibly/probably related to trial product will be followed until the subject has “recovered” or “recovered with sequelae” and all queries have been resolved.

Note: Cases of chronic conditions, cancer or AEs ongoing at time of death (i.e. a subject dies from another AE), can be closed with an outcome of “recovering” or “not recovered”. Cases can be closed with an outcome of “recovering”, when the subject has completed the post-trial follow-up period (1 week after last dosing) and is expected to recover by the Investigator .

All other non-serious AEs will be followed up until the outcome of the event is “recovering”, “recovered”, “recovered with sequelae” or until the end of the post-treatment follow-up period (1 week after last dosing), whichever comes first, and until all queries related to these AEs have been resolved.

The Investigator shall follow up on all SAEs until the outcome of the event is “recovered”, “recovered with sequelae” or “fatal” and until all queries have been resolved, even after trial completion (LSLV). Note: Cases can be closed with an outcome of “recovering” when the subject has completed the trial and is expected by the investigator to recover.

Follow-up actions for all SAEs will be determined after internal review and/or sponsor review.

The follow up information should only include new (updated and/or additional) information that reflects the situation at the time of the Investigator’s signature.

Follow-up information on (S)AEs will be updated using the (S)AE Form. If a non-serious event becomes serious during the follow-up the AE Form and SAE Form have to be used and reporting timelines follow those of a SAE.

Investigators are not obligated to actively seek AEs or SAEs in subjects once they have discontinued from or completed the study. However, if the Investigator learns of any SAE, including a death, at any time after a subject has been discharged from the study, and he/she considers the event reasonably possibly related to IMP or study participation, then the Investigator must promptly notify Lilly.

The Investigator must forward follow-up information on SAEs and if previously non-serious AEs become SAEs to the Sponsor/both, the authorized Sponsor’s delegate for pharmacovigilance (Institute of Clinical Pharmacology) and the Sponsor (contact details are given in Section 9.2).

9.4 Hypoglycaemia

Hypoglycaemia will be recorded and documented using the dedicated Hypoglycaemia Episode form.

Clinical Trial Protocol				
Trial ID	EudraCT-No.	Date	Status / Version-No.	Page
I8B-MC-ITST	2019-003493-13	17 Jan 2020	Final 2.0	56 of 74

The classification and recording of hypoglycaemia in the trial will conform to the current ADA guidance (5).

- Level 1 hypoglycaemic event (Glucose Alert Value): is defined as a symptomatic or asymptomatic event with a measured plasma glucose concentration <70 mg/dL (<3.9 mmol/L) but \geq 54 mg/dL (3.0 mmol/L), [equivalent to a glucose concentration of <63 mg/dL and \geq 49 mg/dL when using whole blood calibrated results]
- Level 2 hypoglycaemic event (Clinically significant hypoglycaemia): is defined as a symptomatic or asymptomatic event with a measured plasma glucose concentration <54 mg/dL (3.0 mmol/L), [equivalent to a glucose concentration of <49 mg/dL when using whole blood calibrated results]

For Level 1 and Level 2 hypoglycaemic events, the Investigator should also assess whether or not the event was accompanied by symptoms of hypoglycaemia (symptomatic or asymptomatic hypoglycaemic event).

- Level 3 hypoglycaemic event (**Severe hypoglycaemia**): A severe event characterized by altered mental and/or physical status requiring assistance. Subjects had either altered mental status, and could not assist in their own care, or were semiconscious or unconscious, or experienced coma with or without seizures, and the assistance of another person to actively administer carbohydrate, glucagon, or other resuscitative actions. These events may be associated with sufficient hypoglycaemia to induce seizure or coma. Plasma or blood glucose measurements may not be available during such an event, but neurological recovery attributable to the restoration of plasma glucose to normal is considered sufficient evidence that the event was induced by a low plasma glucose concentration.

Severe hypoglycaemia will be regarded as SAE and should be recorded on AE and SAE forms.

Any severe hypoglycaemic episode will be accompanied by a narrative giving qualitative descriptions of timing of the episodes in relation to drug exposure, time of onset, time after last drug administration, time after meal, severity, duration, outcome of hypoglycaemia, dose of treatment.

9.5 Pregnancy

Female subjects must be instructed to notify the Investigator immediately if they become pregnant or if they suspect to be pregnant during the trial. The Sponsor has a responsibility to monitor the outcome of all pregnancies reported during the clinical trial.

Pregnancy (maternal or paternal exposure to IMP) does not meet the definition of an AE. However, to fulfil regulatory requirements, any pregnancy should be reported following the SAE process to collect data on the outcome for both mother and foetus.

Clinical Trial Protocol				
Trial ID	EudraCT-No.	Date	Status / Version-No.	Page
I8B-MC-ITST	2019-003493-13	17 Jan 2020	Final 2.0	57 of 74

9.6 Precautions

Normal precautions taken for a human trial, including the provision of emergency equipment, will be taken during this trial. Qualified and well-trained physicians and medical staff will instruct the subjects. During a subject's participation in the trial, the Investigator should ensure that adequate medical care is provided to the subjects for any AEs, including clinically significant laboratory values related to the trial. The Investigator should inform the subject when medical care is needed for intercurrent illnesses of which the Investigator becomes aware.

For further information on safety precautions for LY900014 and Humalog[®], please refer to the current version of the IB and the SmPC for Humalog[®] respectively.

9.7 Complaint Handling

Lilly collects product complaints on investigational products and drug delivery systems used in clinical trials in order to ensure the safety of study participants, monitor quality, and to facilitate process and product improvements.

Subjects should be instructed to contact the Investigator as soon as possible if he or she has a complaint or problem with the IMP so that the situation can be assessed.

Clinical Trial Protocol				
Trial ID	EudraCT-No.	Date	Status / Version-No.	Page
I8B-MC-ITST	2019-003493-13	17 Jan 2020	Final 2.0	58 of 74

10 RISK-BENEFIT ASSESSMENT

Potential Risks

Potential Benefits

Risk-Benefit Assessment

This study will not offer any direct benefits to the subjects participating in the study. The data from previous studies in healthy subjects and subjects with T1DM and T2DM have shown that LY900014 was well tolerated and the adverse drug reactions are in keeping with those reported for Humalog.

Potential risks associated with LY900014, derived from the known risks of insulin lispro (Humalog), are hypoglycaemia, hypersensitivity reactions (localised allergy and/or systemic allergy), undesirable effects at the injection site (injection-site reactions and lipodystrophy), and peripheral oedema (Humalog package insert, 2015).

Notably, across all doses in the studies that have evaluated treprostinil **CCI** as a local vasodilator with or without insulin lispro, there was no clinically significant increase in those AEs associated with systemic absorption of treprostinil, as described in the Remodulin package insert **CCI**. The exposures of treprostinil in LY900014 for participants in ongoing and future clinical studies are expected to be much lower than those observed in the dose ranges previously explored with SC bolus administration of treprostinil. Accordingly, treprostinil exposure in diabetic subjects is generally below the detection limit (0.010 ng/mL) and is substantially lower (at least ~200-fold lower) than those observed in adults for the treatment of PAH. No known potential risks are associated with the microdoses of treprostinil in the LY900014 formulation (LY900014 IB).

In preclinical safety pharmacology and toxicity studies, or clinical pharmacology studies involving LY900014 or treprostinil alone, other than known risks associated with Humalog and Remodulin, no additional risks were identified. Additionally, local and systemic toxicity profiles of Humalog and Remodulin do not suggest the potential for additive or synergistic toxicity.

The study includes inpatient procedures during which participants will be continuously monitored. Induced hyperglycaemia as well as in the event subjects experience hypoglycaemia during the procedures, these will be treated as described in Section 8.8.

More information about the known and expected benefits, risks, SAEs and reasonably anticipated AEs of LY900014 is to be found in the Investigator's Brochure (IB).

Clinical Trial Protocol				
Trial ID	EudraCT-No.	Date	Status / Version-No.	Page
I8B-MC-ITST	2019-003493-13	17 Jan 2020	Final 2.0	59 of 74

11 DATA MANAGEMENT

Data Management is the responsibility of Profil Institut für Stoffwechselforschung GmbH, Neuss Germany.

The complete Data Management process will be described in detail and agreed on in the Data Management Plan for this trial.

Additional information to the Trial Design will be specified in the form SDTM - Trial Design Domain Specifications.

11.1 Case Report Forms (CRFs)

For this trial an electronic CRF (eCRF) will be used.

The Data Management Department of Profil Institut für Stoffwechselforschung GmbH will provide the eCRF. All further information regarding the CRF and the data flow will be described and agreed on in the Data Management Plan.

Clinical Trial Protocol				
Trial ID	EudraCT-No.	Date	Status / Version-No.	Page
I8B-MC-ITST	2019-003493-13	17 Jan 2020	Final 2.0	60 of 74

12 MONITORING PROCEDURES

The monitoring procedures for this trial are described in detail in the Monitoring Manual. The objectives of the monitoring procedures are to ensure that (i) the safety and rights of the trial subjects are respected, (ii) that accurate, valid and complete data are collected, and (iii) that the trial is conducted in accordance with the trial protocol, the principles of GCP and local legislation.

The monitor must be given direct access to the TIF and source documents (original documents, data and records). Direct access includes permission to examine, analyse, verify and reproduce any record(s) and report(s) that are important to evaluation of the clinical trial.

Key tasks of the monitor include to verify the presence of informed consent, the adherence to the inclusion/exclusion criteria, the documentation of SAEs, and the recording of all safety and efficacy variables. The monitor will also confirm the completeness of subject records, the adherence to the protocol and the progress in subject enrolment.

Because no information that could reveal the identity of subjects may ever be removed from the trial site, the monitor will visit the site at regular intervals to perform these monitoring tasks. Other contact between the Investigator and monitor will be maintained as required through telephone calls and e-mail. The Investigator and/or key members of staff involved in the trial must be available to assist the monitor during all visits.

Site Initiation Visit

During the Site Initiation Visit (SIV) the Sponsor and/or monitor will review information on the IMP, the protocol, the CRFs and other key aspects of the trial with the Investigator and the key members of staff involved in the trial. The topics of the SIV are documented in a SIV report made available to the Investigator. Sponsor's documentation on the SIV (e.g. power point presentation) should be filed by the Investigator.

Source Data Verification

Details on source data verification are specified in the Monitoring Manual.

Clinical Trial Protocol				
Trial ID	EudraCT-No.	Date	Status / Version-No.	Page
I8B-MC-ITST	2019-003493-13	17 Jan 2020	Final 2.0	61 of 74

13 STATISTICAL CONSIDERATIONS

Eli Lilly will be responsible for the derivation of the PK and GD endpoints and will provide the derived PK and GD endpoints to Profil Institut für Stoffwechselforschung GmbH, Neuss, Germany. Profil will be responsible for the statistical analysis of the endpoints. The statistical planning and conduct of the analyses of the data will follow the principles defined in relevant ICH guidelines and the Sponsor's and Profil's SOPs. A general description of the statistical methods to be used is given in this chapter, specific details will be provided in the SAP. All statistical analyses performed at Profil will use SAS® (SAS Institute Inc., Cary, North Carolina, United States of America [USA]), Version 9.4 or later. PK parameters, analysed by Eli Lilly, will use standard noncompartmental methods of analysis (Phoenix® version 6.3 or above).

13.1 Sample Size Calculation

A sample size calculation was performed based on the primary endpoint and an assumption of an SD of the primary endpoint of 78 min (crossover mean square error of ~55). A sample size of 24 subjects who complete the trial is considered to be sufficient to evaluate a difference between the treatments of 32 minutes with a power of 80%. Discontinued subjects may be replaced to ensure that 24 subjects complete the trial. To take account of discontinued subjects, 28 subjects will be enrolled in the trial. A replacement subject will be assigned to the same treatment sequence as the patient being replaced.

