After the insulin bolus given with the evening meal, no correction boli should be given subcutaneously. Overnight, the basal insulin infusion rate will be running and a target fasting plasma glucose level in the range of 126 ± 20 mg/dL will be aimed for. The basal insulin infusion rate will be fixed to a single hourly rate from at least – 3 hours prior to basal insulin suspension. Basal insulin suspension will be performed between 8 and 10 hours after the dinner meal on Day 1. On-site glucose measurements **CCI** will be performed regularly and frequently to follow the rise in plasma glucose concentration above 240 mg/dL and blood samples for PK analysis will be taken to analyse the decline in circulating insulin levels. As soon as a glucose measurement above the high glucose threshold has been measured and the result has been confirmed by a second measurement a correction bolus will be administered via a subcutaneous injection in the periumbilical region using an insulin syringe. In addition, a plasma sample for ketone concentration will be taken during this time. Regular and frequent sampling for PK, ketone and glucose analysis continues and the time to reach a $PG \leq 140$ mg/dL will be documented.

After completion of basal insulin suspension procedures at Visit 3 Day 2, subjects will be switched back to their usual diabetes therapy and come back to the trial centre for the final examination.

Clinical Trial Protocol				
Trial ID	EudraCT-No.	Date	Status / Version-No.	Page
I8B-MC-ITST	2019-003493-13	17 Jan 2020	Final 2.0	13 of 74

Statistical methods:

A sample size of up to 28 patients with T1DM will be enrolled and at least 24 subjects should complete this trial to achieve study objectives. The sample size is considered sufficient to evaluate a difference in the primary endpoint between the treatments of 32 minutes with a power of 80%. Discontinued subjects may be replaced to ensure that 24 subjects complete the trial. A replacement subject will be assigned to the same treatment sequence as the subject being replaced. .

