5 TRIAL DESIGN

5.1 Type of Trial

Single center, randomized, two-treatment, subject- and investigator-blinded, 2-period cross-over trial in subjects with T1DM.

A schematic trial overview is given in Section 2, [Figure 1](#).

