All analyses will be fully detailed in the SAP.

Unless otherwise noted, all tests of treatment effects will be conducted at a 2-sided alpha level of 0.05, and CIs will be calculated at 95%, 2-sided. Additional exploratory analyses of the data will be conducted as deemed appropriate. Study results may be pooled with the results of other studies for population PK analysis purposes to avoid issues with post-hoc analyses and incomplete disclosures of analyses.

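### The stated 80% power does not follow from the plan's own inputs: 24 completers give about 48% power for 32 minutes, and 80% needs about 48 to 49.

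*Protocol*

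**What the plan says.** The design is a two-treatment, two-period crossover (Protocol 5.1). Protocol 13.1 bases the sample size on the primary endpoint, time to recovery from hyperglycaemia, and assumes "an SD of the primary endpoint of 78 min (crossover mean square error of ~55"). It then states: "A sample size of 24 subjects who complete the trial is considered to be sufficient", specifically "sufficient to evaluate a difference between the treatments of 32 minutes with a power of 80"%. On dropout it says: "To take account of discontinued subjects, 28 subjects will be enrolled in the trial". Protocol 6.6 allows up to four more replacements, to a maximum of 32.

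The synopsis repeats the claim ("difference in the primary endpoint between the treatments of 32 minutes with a power of 80"%), and SAP 3.3 carries the same SD, error, number, difference and power. Protocol 13.2 sets the test level: "all tests of treatment effects will be conducted at a 2-sided alpha level of 0.05". The primary analysis (Protocol 13.4.1, SAP 5.7) is a crossover mixed model on the untransformed endpoint, fitted separately for Day 1 and Day 2. Neither document gives the formula, the software or a within-subject correlation for the calculation.

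**The concern.** A crossover error of 55 min implies an SD of about 78 min for the within-subject treatment difference. With 24 subjects, a 32-minute effect is then only about two standard errors, which corresponds to roughly even odds of significance, not 80%.

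This is the only quantitative justification for the sample size. If it is wrong, a true 32-minute benefit on a given day would be missed about half the time, and a non-significant result could be read as evidence from an 80%-powered comparison. The type I error and the treatment estimate are not affected.

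**Working it through.** **Inputs.** Difference δ = 32 min, SD 78 min, crossover error about 55, N = 24 completers in total (Protocol 13.1, SAP 3.3). Two-sided α = 0.05 (Protocol 13.2, SAP 5.5.2). The allocation ratio is not stated; equal sequences (12 + 12) are assumed.

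**What 55 measures.** 78/√2 = 55.15. A literal mean square of 55 min² would be an error SD of √55 = 7.4 min, which gives power of about 100% and cannot be squared with an SD of 78. So 55 is in minutes, and a crossover-model error in minutes is the root MSE, i.e. the within-subject SD. The SD of the within-subject difference is 55 × √2 = 77.8, in effect 78. The result is the same whether 78 is the SD of the differences or the endpoint SD with within-subject correlation 0.5.

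**Power at N = 24.**
- SE = SD_diff/√N = 78/√24 = 15.92 min
- Noncentrality = 32/15.92 = 2.01
- df = N − 2 = 22, critical t = 2.074
- Power (noncentral t) = 48.5%; with root MSE exactly 55, 48.7%
- Normal approximation: Φ(2.01 − 1.96) = 52.0%

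The stated 80% is not reproduced.

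**Other sample sizes** (SD_diff 78, noncentral t):

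| N analysed | Power for 32 min |
|---|---|
| 20 | 41% |
| 24 (planned completers) | 48.5% |
| 28 (planned enrolment) | 55% |
| 32 (maximum) | 61% |
| 48 | 79.5% |
| 49 | 80.3% |
| 50 (first even number above 80%) | 81.1% |

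**What 24 completers can do on these inputs.**
- Difference detectable with 80% power: 46.7 min
- Expected 95% CI half-width: 2.074 × 15.92 = 33.0 min, slightly more than the 32-minute target
- Error needed for 80% power at 32 min: SD_diff about 53.5, root MSE about 53.5/√2 = 37.8

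**Attempts to recover 80%.**

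| Reading | Power |
|---|---|
| One-sided 0.05, N = 24 | 62% |
| 78 as within-subject SD (SD_diff 110) | 27% |
| Parallel-group formulas | 17–52% |
| Root MSE 55, 24 per sequence (48 in total) | 79.5–79.7% |
| 55 as SD of the difference, N = 24, t-test | 77.8% |
| 55 as SD of the difference, N = 24, normal approximation | 81.3% |

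Only the last three come near the plan's figure. By the normal formula, the last gives N = (1.96 + 0.84)² × 55²/32² = 23.2, rounded up to 24.

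**The case against.** The strongest counter-argument is that the text does not fix a single reading. Protocol 13.1 calls 78 the SD of the endpoint, not of the difference, and gives no correlation. If 78 is the endpoint SD and the within-subject correlation is 0.75, the SD of the differences is 78 × √(2 × 0.25) = 55.15. The ratio 78/55 = √2 therefore fits this reading too, and the normal formula then returns exactly 24. The CI half-width would be about 23 min. The label on 55 is wrong on any reading, so perhaps little weight should rest on it.

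Part of this stands: the √2 ratio alone does not decide the matter, and the documents cannot show how the error arose. But this reading needs a correlation of 0.75 that neither document states. It also requires the crossover error to be something other than the residual of the crossover model, which enters the standard error with a factor √2. Even then, the t-test implied by the planned model gives 77.8% at 24 and needs 26. The per-sequence reading contradicts the plain statement of 24 subjects completing the trial.

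A further fair point is that 48% applies to each day's comparison. The plan has two primary comparisons, so it is not the chance that at least one succeeds. The 80% in Protocol 13.1 is also for a single comparison, so the contrast between the two figures is like with like.

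**Conclusion.** The concern holds. On the standard meaning of a crossover error, 24 completers give about 48% power for 32 minutes per comparison, more than 30 percentage points below the stated 80%. No enrolment permitted by the protocol reaches 80%; that takes 49 completers (50 with equal sequences, while 48 gives 79.5%).

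This rests on 55 being the root MSE, 24 being a total, a two-sided 0.05 test and equal sequences. On the reading kindest to the plan, the planned t-test still falls about 2 points short and 55 is still mislabelled, so the passage needs correction either way.

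The number analysed may also fall below 24. Completers with unequal doses or meals are excluded (Protocol 13.4.1), and SAP 5.7 also drops both periods of a day for anyone needing rescue insulin. Replacement covers only discontinued subjects. With 20 analysed and the same SD, power would be 41%; the documents give no expected exclusion rate.

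**What to change.** Correct Protocol 13.1, the synopsis and SAP 3.3 together:

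- State what 78 and 55 each measure, and that 24 is the total across both sequences. Call 55 the root MSE (within-subject SD).
- State that 24 completers give about 48% power for 32 minutes, or equivalently 80% power for about 47 minutes, per day, at two-sided 0.05.
- If a smaller error was intended (root MSE about 38, SD of differences about 53), give that value and its basis instead.

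The cost is wording in two documents and a less favourable stated power. The correction itself requires no additional subjects.

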13.2 Selection of Subjects for Analyses

The following analysis sets are defined in accordance with the ICH-E9 (6) guidance:

Full Analysis Set (FAS)

The full analysis set (FAS) is based on the intention-to-treat principle and includes all subjects who were treated with IMP. Subjects will contribute to the evaluation 'as randomized'.

Modified FAS (mFAS)

The modified FAS includes all subjects of the FAS who complete the study according to the sequence/treatment to which they are randomized. Subjects will contribute to the evaluation 'as randomized'. Primary and secondary statistical analyses of PK and GD parameters will be conducted on the set of subjects who complete all treatment periods with the same dose and meal intake **CCI**

Safety Analysis Set

The safety analysis set includes all enrolled subjects, whether or not they fulfilled all protocol requirements. Subjects in the safety set will contribute to the evaluation 'as treated'. The safety analysis will be based on the safety analysis set.

Clinical Trial Protocol				
Trial ID	EudraCT-No.	Date	Status / Version-No.	Page
I8B-MC-ITST	2019-003493-13	17 Jan 2020	Final 2.0	62 of 74

Before data are released for statistical analysis, a blinded review of all data will take place to identify protocol deviations that may potentially affect the results. This review will be performed without revealing which IMP the subjects are assigned to. The blinding of the IMPs will be maintained for everyone involved in allocating subjects to the analysis sets until data are released for statistical analysis. Obviously erroneous data points may be excluded from the analyses or re-analysed (in case of e.g. serum concentrations). The decision to re-analyse or exclude data points from the statistical analysis is the joint responsibility of the Sponsor, the Principal Investigator and the Trial Statistician.

The subjects or observations to be excluded and the reason for their exclusion will be documented and signed by those responsible prior to database lock. The documentation will be stored together with the remaining trial documentation. The subjects and observations excluded from analysis sets, and the reason for this, will be described in the clinical study report.

Subjects withdrawn from the trial will be listed including the primary reason for withdrawal.

If deemed necessary further endpoints and/or analyses may be added to the SAP. Only analyses not specified in the SAP will be considered as post-hoc analyses.

All analyses will be fully detailed in the SAP.

Unless otherwise noted, all tests of treatment effects will be conducted at a 2-sided alpha level of 0.05, and CIs will be calculated at 95%, 2-sided. Additional exploratory analyses of the data will be conducted as deemed appropriate. Study results may be pooled with the results of other studies for population PK analysis purposes to avoid issues with post-hoc analyses and incomplete disclosures of analyses.

